11.2 Sample Size Considerations

The primary outcome used for power analysis is the area under the curve for 12 hours (AUC12) following 6 mg/kg of ganciclovir. In a one-way ANOVA design, we would like to compare the means of 4 groups (see below) with sample sizes of approximately 8, 8, 8, and 8 (32 total subjects enrolled across the four cohorts). If the means of the AUC12 of the 4 groups are 20, 20, 30, and 35 assuming a common standard deviation of 10, these mean differences (equivalent to an effect size of 0.72) will be detected at 83% power using an F test with 0.05 level of significance. In order to look at other possible scenarios, we provide the table below that looks at other standard deviation values, its corresponding effect size given the differences in means as described above, and the power of detecting such a difference/effect size. If estimating the AUC without regard to the groups, the margin of errors associated with a 95% confidence interval assuming different standard deviation values and a sample size of 32 are given in the table below.

Standard Deviation	S=8	S=9	S=10	S=11
Effect Size	0.81	0.72	0.64	0.59
Power	96%	91%	83%	75%
Margin of Error	2.33	2.62	2.91	3.20

The above parameter values were hypothesized based on results from other studies.^{25,34} It is worth noting that there are no PK data in this population and the results are likely to be different from other studies due to the maturational changes.

Following enrollment, subjects will be stratified by gestational age and by chronologic age as follows: 1) \leq 27 weeks 6 days gestational age at birth and \leq 30 days chronologic age at study enrollment; 2) \leq 27 weeks 6 days gestational age at birth and $>$ 30 days chronologic age at study enrollment; 3) \geq 28 weeks 0 days gestational age at birth and \leq 30 days chronologic age at study enrollment; 4) \geq 28 weeks 0 days gestational age at birth and $>$ 30 days chronologic age at study enrollment. The total sample size across these four cohorts is 32 subjects. Enrollment of an additional 2-3 subjects may be allowed for operational reasons. If the 32

subjects enrolled are not balanced across the 4 groups, we instead will look at the correlation between gestational age at birth. With 32 subjects, the margin of errors of a 95% confidence interval for estimating the correlation given the observed correlation values are given below.

Correlation	0.4	0.5	0.6	0.7
Margin of Error	0.6	0.542	0.47	0.38

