11.4 Final Analysis Plan

Primary analysis: To compare the ganciclovir pharmacokinetics and pharmacodynamics as measured by AUC₁₂ in premature infants with postnatally or congenitally acquired CMV infection differ from those in term neonates and older infants, we will construct 95% confidence intervals around the mean AUC₁₂ for the subjects in this study and compare these means across the groups. If there are not enough subjects in the groups, we will use the actual gestational age and correlate it with the AUC₁₂ by computing correlation coefficients and a fitting regression model. Additional pharmacokinetic parameters that compose analyses for secondary endpoints include Cmax, T1/2, CL, and VD. For measures that are repeated over time, we will utilize mixed models for repeated measures. In addition to being able to compare these outcomes for the different groups, we can also look into how these measures change over time and adjust for covariates.

Ganciclovir pharmacokinetic parameters will initially be determined using non-compartmental analysis (WinNonlin v5.3) for each individual subject. The parameters (AUC₁₂, CL, Vd, etc.) will be summarized and further used for exploratory pharmacodynamic analysis. We will also apply pharmacokinetic models to the concentration-time data, either individually or using a population approach. We may also pool these data with prior CASG 109 PK data in order to have a more robust covariate analysis across a wider range of ages.

The second pharmacokinetic analysis will utilize either population pharmacokinetic or individual modeling approaches, depending upon how much data we actually are able to collect and the nature of those data. Concentration-time data will be analyzed using nonlinear mixed-effects in ADAPT 5.0. If a population approach is employed, this will give us the opportunity to explore

relationships between ganciclovir exposure and multiple covariates, such as gestational age, weight, renal function, etc.

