APPENDIX B

DATA ANALYSIS PLAN

Study Hypotheses

Our primary hypothesis is that ganciclovir pharmacokinetics and pharmacodynamics in premature infants with postnatally or congenitally acquired CMV infection differ from those in term neonates and older infants.

Sample Size Considerations

The primary outcome used for power analysis is the area under the curve for 12 hours (AUC12) following 6 mg/kg of ganciclovir. In a one-way ANOVA design, we would like to compare the means of 4 groups with sample sizes of 8, 8, 8, and 8. If the means of the AUC12 of the 4 groups are 20, 20, 30, and 35 assuming a common standard deviation of 10, these mean differences (equivalent to an effect size of 0.72) will be detected at 83% power using an F test with 0.05 level of significance. In order to look at other possible scenarios, we provide the table below that looks at other standard deviation values, its corresponding effect size given the differences in means as described above, and the power of detecting such a difference/effect size.

Standard Deviation	S=8	S=9	S=10	S=11
Effect Size	0.81	0.72	0.64	0.59
Power	96%	91%	83%	75%

The above parameter values were hypothesized based on results from other studies.^{25,34} It is worth noting that there are no PK data in this population and the results are likely to be different from other studies due to the maturational changes.

Subjects will be stratified by gestational age and by chronologic age as follows: 1) \leq 27 weeks 6 days gestational age at birth and \leq 30 days chronologic age at study enrollment; 2) \leq 27 weeks 6 days gestational age at birth and $>$ 30 days chronologic age at study enrollment; 3) \geq 28 weeks 0 days gestational age at birth and \leq 30 days chronologic age at study enrollment; 4) \geq 28 weeks 0 days gestational age at birth and $>$ 30 days chronologic age at study enrollment.

Data will be collected on standardized case report forms. Standard non-compartmental techniques will be used initially to estimate pharmacokinetic parameters derived from the ganciclovir concentration-time data. The resource utilized for pharmacokinetic analysis is WinNonlin version 5.3, Pharsight Corporation, Mountain View, CA.

Planned Interim Analyses

There are no planned interim analyses or safety reviews for this trial.

Final Analysis Plan

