Primary analysis: To compare the ganciclovir pharmacokinetics and pharmacodynamics as measured by AUC12 in premature infants with postnatally or congenitally acquired CMV infection differ from those in term neonates and older infants, we will utilize mixed models for repeated measures. Additional pharmacokinetic parameters that compose analyses for secondary endpoints include Cmax, T1/2, CL, and VD. In addition to being able to compare these outcomes

for the different groups, we can also look into how these measures change over time and adjust for covariates.

Ganciclovir pharmacokinetic parameters will initially be determined using non-compartmental analysis (WinNonlin v5.3) for each individual subject. The parameters (AUC₁₂, CL, Vd, etc.) will be summarized and further used for exploratory pharmacodynamic analysis. We will also apply pharmacokinetic models to the concentration-time data, either individually or using a population approach. We may also pool these data with prior CASG 109 PK data in order to have a more robust covariate analysis across a wider range of ages.

The second pharmacokinetic analysis will utilize either population pharmacokinetic or individual modeling approaches, depending upon how much data we actually are able to collect and the nature of those data. Concentration-time data will be analyzed using nonlinear mixed-effects in ADAPT 5.0. If a population approach is employed, this will give us the opportunity to explore relationships between ganciclovir exposure and multiple covariates, such as gestational age, weight, renal function, etc.

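### Protocol and SAP Appendix B name different primary analyses of AUC12, and the protocol's fallback has no numeric trigger, is absent from Appendix B and does not commit to chronologic age

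*SAP*

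**What the plan says.** **Primary analysis.** Under that label, protocol 11.4 says "we will construct 95% confidence intervals around the mean" AUC12 "for the subjects in this study and compare these means across the groups". It gives mixed models a separate role: "For measures that are repeated over time, we will utilize mixed models for repeated measures". SAP Appendix B opens its primary-analysis paragraph almost identically, but the method is the mixed model: "differ from those in term neonates and older infants, we will utilize mixed models for repeated measures". No intervals for mean AUC12 appear there. Both documents size the study as a one-way ANOVA; in Appendix B the aim is to "compare the means of 4 groups with sample sizes of 8, 8, 8, and 8".

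**Profiles per infant.** Protocol section 4 requires one profile. A second may follow in Period 4, only if the treating physician requests it and the infant weighs at least 575 g.

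**Fallback.** The protocol states it twice. Section 11.2: if the 32 "subjects enrolled are not balanced across the 4 groups, we instead will look at the correlation between gestational age at birth", with the second variable of the correlation left unnamed. Section 11.4: "If there are not enough subjects in the groups, we will use the actual gestational age and correlate it with the" AUC12, adding a regression model whose terms are not listed. Appendix B has no fallback.

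**Chronologic age.** It is one of the two factors that define the four cohorts. Protocol 11.4 and Appendix B both allow covariate adjustment, an open-ended covariate list for the population model, and possible pooling with CASG 109 data. All of these are optional, and none commits to chronologic age.

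**Group cap.** Section 3.3.4.2 of SAP Appendix C, a draft software specification, closes a group at 8 subjects.

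**The concern.** AUC12 is the primary endpoint, so the plan should say which analysis gives its primary result, on which data, and when another analysis takes its place. Two documents that name different methods under the same label leave the first two open. A trigger without a number leaves the third to be decided after AUC12 values are known. The study is open-label and individual AUC values go back to sites (protocol section 4), so that is a practical possibility.

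The fallback also drops one of the two design factors. The protocol's own evidence of rapid maturation concerns postnatal age: in section 2.1, AUC12 fell by almost half over 30 days in five neonates. The fallback is meant for unbalanced or thin cohorts, and imbalance is what can associate the two ages. The gestational-age slope would then carry part of a chronologic-age effect.

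**Working it through.** **1. The plan's own power figure.** Inputs from protocol 11.2 and Appendix B: means 20, 20, 30, 35; SD 10; 8 per group; alpha 0.05. The grand mean is 26.25.

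- Noncentrality = 8 × [(20−26.25)² + (20−26.25)² + (30−26.25)² + (35−26.25)²] / 10² = 8 × 168.75 / 100 = 13.5.
- With 3 and 28 degrees of freedom, power is 83.1%, which reproduces the stated 83%.

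The calculation uses one AUC12 value per infant and a four-group comparison. That is the protocol's primary analysis.

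**2. When the two methods differ.** With one profile per infant there is nothing repeated, and a mixed model with cohort as the factor gives the same group comparison as the ANOVA. They part only when second profiles exist. Those come from infants still on treatment at Study Assessment Days 18–24 whose physician asked for one. Protocol 2.1 puts treatment at generally two to four weeks, so they may be few.

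**3. The cap against the imbalance provision.** Four groups closed at 8 give at most 4 × 8 = 32. Apart from replaced subjects and the 2–3 extra allowed, 32 enrolled under the cap must be 8/8/8/8, and the imbalance foreseen in protocol 11.2 could not arise.

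**4. Bias of a slope on gestational age alone.** Assumptions, none of them in the documents:

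- SD 10; mean AUC12 30 at ≤ 30 days and 20 at > 30 days, so the age effect is 10; no true gestational-age effect.
- Gestational age uniform over 23w0d–27w6d (mean 25.43, width 4.857 weeks) or 28w0d–31w6d (mean 29.93, width 3.857), and unrelated to chronologic age within a stratum.

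For equal-sized gestational strata, let Δp be the proportion aged ≤ 30 days in the older-gestation stratum minus that in the younger.

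- Covariance of gestational age with the age factor = 0.25 × (29.93−25.43) × Δp = 1.125 Δp.
- Variance of gestational age = 0.25 × 4.5² + (4.857² + 3.857²)/24 = 5.06 + 1.60 = 6.67.
- False slope ≈ 10 × 1.125 Δp / 6.67 = 1.69 Δp per week.

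| Cohorts 1/2/3/4 | Total | Δp | Formula | Simulated |
|---|---|---|---|---|
| 8/8/8/8 | 32 | 0 | 0 | 0 |
| 6/8/8/6 | 28 | 8/14 − 6/14 = 0.143 | +0.24 | about +0.25 |
| 5/8/8/5 | 26 | 8/13 − 5/13 = 0.231 | +0.39 | +0.4 |
| 5/11/11/5 | 32 | 11/16 − 5/16 = 0.375 | +0.63 | +0.6 |
| 4/12/12/4 | 32 | 12/16 − 4/16 = 0.5 | +0.84 | +0.86 |

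Adding the ≤ 30/> 30-day factor brings the simulated bias to 0 in every row. The sign reverses in mirror patterns (8/5/5/8: −0.4). Doubling the age effect to 20 doubles each entry.

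**5. Precision.** Mean 95% half-width of the slope under the same assumptions, gestational age alone against adjusted: 1.58 v 1.41 at 8/8/8/8, 1.70 v 1.53 at 6/8/8/6, 1.77 v 1.62 at 5/8/8/5. In these cases the age term narrows the interval.

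**The case against.** **The methods hardly differ.** Both documents announce the same contrast and the same group comparison, and a mixed model can also give group means with 95% intervals. This largely stands. A reader might infer that the two documents would yield different primary results. They do not, unless second profiles exist; what is left is which method is named as primary and how those profiles enter.

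**The bias is slight.** Within a cap of 8 and with modest shortfalls, this stands: +0.25 against a half-width of 1.70 at 6/8/8/6. A reader might infer an inflated false-positive rate. The plan states no test of this slope; protocol 11.2 offers only "the margin of errors of a 95% confidence interval for estimating the correlation". If it were tested at 0.05, rejection would be 4% at 6/8/8/6 and 5–6% at 5/8/8/5. The larger biases need 32 infants spread beyond the cap, which protocol 11.2 allows for, or cohorts of 3–4.

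**Age can already be adjusted for.** Covariate adjustment and pooling with CASG 109 would permit it. Neither document requires it.

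**A threshold cannot be read from the plan.** A reader might derive fewer than 5 infants per cohort, because one cohort's own interval at n = 4 has half-width 15.9, more than the largest planned difference of 35 − 20 = 15. That sets a single mean against a difference and ignores the plan's common SD. Pooled at 4/8/8/4 (20 df, t = 2.086), the half-width is 2.086 × 10/√4 = 10.4 for a mean, and 2.086 × 10 × √(1/4 + 1/8) = 12.8 or 2.086 × 10 × √(1/4 + 1/4) = 14.75 for a difference, all below 15. Power gives no threshold either. The documents do not map the planning means to cohorts. If those of cohorts 2 and 3 are swapped, the four-group test at 4/8/8/4 keeps 61% power, while the adjusted gestational-age slope has about 8%.

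**Conclusion.** The point holds, as a specification gap that should be closed. The primary analyses are named differently, Appendix B is silent on optional profiles, neither trigger has a number, and the fallback does not commit to chronologic age. These follow from the text and need no simulation.

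The consequence is moderate and conditional. Without second profiles the two primary methods agree on the group comparison. A gestational-age correlation is valid as a description. It is confounded only if the two ages are associated in the enrolled sample, and the documents do not give their joint distribution. The false slopes, from about +0.25 to +0.9 per week, rest on an assumed 10-unit age effect, SD 10 and the age distributions listed above.

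The fallback's absence can be stated for Appendix B only, since some SAP pages were not available. The cap of 8 stands in a draft specification, so its conflict with protocol 11.2 is something to reconcile and not proof of how enrollment ran.

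**What to change.** 1. In protocol 11.4 and Appendix B, name one primary analysis: 95% intervals for mean AUC12 and the four-group comparison, from the first, mandatory profile. Keep mixed models and second profiles for secondary analyses of change over time.
2. Replace the two triggers with one numeric rule on cohort sizes that covers both imbalance and small cohorts. The sponsor should choose it and fix it before AUC12 data are seen.
3. Make the fallback a regression of AUC12 on gestational age at birth plus chronologic age, for example the ≤ 30/> 30-day factor. Report both coefficients, since either age may carry the effect. Put it in Appendix B as well.
4. Reconcile the draft specification's cap of 8 with protocol 11.2's provision for 32 unbalanced subjects.

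**Cost.** Wording only; date of birth is already collected (protocol 8.1.1). The age term uses one degree of freedom. If age has no effect, the slope's interval widens by about 0.5% at 8/8/8/8, 1% at 6/8/8/6, 3% at 5/8/8/5 and 10% at 3/8/8/3. The form of the age term is also an assumption: if the truth is a step at 30 days and age is entered linearly, a false slope of about +0.1 remains at 5/8/8/5 and +0.2 at 3/8/8/3.

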APPENDIX C

USER REQUIREMENT SPECIFICATIONS DRAFT

Specifications

1. User Database Design and Functionality

- 1.1. The user database has four primary purposes:
 - 1.1.1 To provide a secure mechanism to control password access and permissions.
 - 1.1.2 To provide the ability to generate and control enrollment and/or randomization (including study drug assignment) and protocol specific emails to the correct research personnel.
 - 1.1.3 To provide a repository for maintaining contact information for investigators and key research staff.
 - 1.1.4 To generate distributions lists per protocol from the database.
- 1.2. Fields required for the user database are listed below:
 - User's name
 - Selection of title of user (PI, Sub I, study coordinator, regulatory, monitor, laboratory personnel, administrator, other)
 - User's email address
 - Protocol(s) user is permitted access to Institution site staff member associated with (site #)
- 1.3. Design of the user database
 - 1.3.1 Design data entry page to include contact information fields listed in 10.1.2. and when required, assignment of permissions
 - 1.3.2 Design the contact database to meet the requirements listed in 10.1.1
- 1.4. Functionality of the user database will be the following:
 - 1.4.1 Entry of contact information will be managed remotely by the CU PCII or designee.
 - 1.4.1.1 The PCII or designee will be given permissions to assign a user access by the PD or designee.
 - 1.4.1.2 After entering user information, the PCII or designee will assign a user name and a temporary password.
 - 1.4.1.3 After the user enters the system with the user name and temporary password, the user will be prompted to create his/her own confidential password.
 - 1.4.1.4 If the user forgets his/her password, she/he will contact the PCII or designee to receive a temporary password in order to re-identify a confidential password.
 - 1.4.1.5 Types of permissions:
 - Access to subject enrollment/randomization and eCRF completion

- Access to print study-specific documents
- Access for monitoring purposes
- Access to unlock eCRF for data query resolution
- Access to enter specimen results
- Access for user certification of eDES usage
- Access to generate queries

- 1.4.2 Email notifications (see 1.4.5) will be sent to designated study personnel. These personnel will be identified by the PD and or designee.
- 1.4.3 The PCII or designee will be able to de-activate users when personnel discontinue participation in the protocol.
- 1.4.4 The content of the email alerts and notifications will be drafted by the PD or designee
- 1.4.5 Types of notifications
 - 1.4.5.1 Enrollment notification to site
 - 1.4.5.2 Shipping of PK samples notification to CU and to pharmacology lab
 - 1.4.5.3 Shipping of virology samples notification to CU and virology lab
 - 1.4.5.4 PK eCRF field change notification to Pharmacologist
 - 1.4.5.5 Protocol deviation alert to CU
 - 1.4.5.6 Shipping receipt acknowledgment alert for Virology specimen
 - 1.4.5.7 Shipping receipt acknowledgment alert for PK specimens
 - 1.4.5.8 PK result notification
 - 1.4.5.9 Data field unlock request
 - 1.4.5.10 Transfusion alert

2. End User Training and Certification

2.1. Purpose

- 2.1.1 To build an electronic system that will include a means for remote data entry by end user, email notifications when required, interface use with ancillary services and a system for monitoring.
- 2.1.2 To verify the functionality of the eDES
- 2.1.3 To assure user is capable of using the eDES.

2.2. Process for verifying the eDES

- 2.2.1 Comprehensive testing will take place reviewing and testing functionality of each feature in the eDES.
- 2.2.2 PD and designees will be granted permission to test the system when system/functions are complete.
- 2.2.3 Each eCRF field will be tested to determine if the assigned rules are functioning as required.
- 2.2.4 At least three UAB CU clinical personnel will test the system by reviewing and testing each field of the eCRF by entering mock data, assuring functionality is as required and confirming that the rules are correct. Additionally, DCC staff will also test the fields.

- 2.2.5 After completion of the testing of the eCRF fields, email notifications, ancillary service users, the PD or designee, MITS and DCC will confirm that eCRF and eDES meets specifications, design and functional requirements.
- 2.2.6 The PD will sign off after confirmation by all entities that the system meets the URS.

2.3. Process for certifying end users: Clinical Sites

- 2.3.1 Central Unit staff will prepare 3 mock sets of Source Document Worksheets (SDW) (test packets). Each set will be assigned a number: #1, #2 and #3.
- 2.3.2 Three staff (1 from the CU, 1 from Programming group, 1 from the Data Management group) will be identified to enter each of the three test packets.
- 2.3.3 A DCC biostatistician will compare the records entered by all 3 users to the corresponding packet. Errors and problematic fields will be identified and corrections made as determined necessary by the CU clinical administrators, MITS and DCC.
- 2.3.4 Following successful completion of the 3 test packets entry and 100% assurance of system functionality, the ‘gold records’ are established. Gold records are used to compare the records entered by a person undergoing eDES certification consequently determining if the person passed or failed the certification.
- 2.3.5 The PD or designee will create a user manual for end users (*eDES User Manual*)
- 2.3.6 Users identified by the PD or designee will be provided with the *eDES User Manual* and provided with access for certification by the PCII or designee, as needed.
- 2.3.7 The designated Biostatistician will identify successful data entry certification as less than or equal to 0.5% error rate.
- 2.3.8 The CSA or designee will provide user with #1 test packet. The PD, PCII, or designee will assign data entry permissions to the user.
- 2.3.9 Following entry of the #1 test packet into the eDES, a DCC Biostatistician will report to the PD or designee if the user’s error rate was no greater than 0.5%. (The DCC will also provide a list of errors.) The PD or designee will generate to the user a certificate of successful entry of the test packet.
- 2.3.10 If the user fails to successfully enter #1 test packet (*i.e.*, error rate was greater than 0.5% error rate), the list of errors will be reviewed by the PD or designee with the user, and the PD or designee will re-train the user on how to avoid those errors. The PD or designee will provide the user with #2 test packet.
- 2.3.11 If the user fails to successfully enter #2 test packet, the process in 2.3.11 will be repeated. The user will be provided with #3 test record. If #3 test packet is not successfully entered, the CU administrators and the DCC will discuss options for the clinical site. These may include requesting another

person at the site assume the site's data entry responsibilities, or request the user who failed data entry begin the certification process again in 1 month. A final option will be for the CU administration to provide an hour long training session on use of the eDES to the person who has failed certification three times. Note that a site will be activated only if at least one staff member has successfully showed the capability to correctly enter data (*i.e.*, passed certification).

- 2.4. Process for certifying end users: Monitors
 - 2.4.1 A test site will be created for the monitors to demonstrate the use of the monitor function of the eDES.
 - 2.4.2 The PD or designee in collaboration with MITS will create a user manual for the monitors use (*eDES User Manual: CRA*)
 - 2.4.3 The CRA will review the *eDES User Manual: CRA* and will review the system with the PD or designee.
 - 2.4.4 The PD or designee will document the training.
- 2.5. Process for certifying end users: CU
 - 2.5.1 A mock site will be created for the CSA and designee to test and practice entry of data queries into the eDES system and to test opening and locking the system for site data entry.
 - 2.5.2 MITS will create a user manual for the CU Administration use (*eDES User Manual: CU Administrators*).
 - 2.5.3 The PD and designee will review the *eDES User Manual: CU Administrators* and will review the system with MITS.
 - 2.5.4 MITS will document training of the CU Administration.

3. Enrollment Design and Functionality

- 3.1. Purpose of the enrollment component of the eDES system is the following:
 - 3.1.1 To allow for remote enrollment of subjects who meet study entry criteria.
 - 3.1.2 To notify all key personnel in a timely manner of successful enrollment.
 - 3.1.3 To disable enrollment in a cohort if enrollment is completed for that cohort.
 - 3.1.4 Patient Identification (PID) numbers will be assigned: screening PID will be assigned after selecting New Subject. Enrollment process (completion of inclusion/exclusion criteria) can begin after PID #1 (4 alphanumeric characters) is assigned. Enrollment PID #2 (5 numbers) will be assigned when subject successfully meets protocol required eligibility criteria for enrollment.
- 3.2. Design of the enrollment component of the eDES
 - 3.2.1 The inclusion and exclusion criteria will match the protocol.
 - 3.2.2 The criteria will be answered 'yes', 'no', 'NA', and/or have defined ranges, if number values for study entry are required. The PD or designee will manage and oversee that the design of the entry criteria match the protocol eligibility requirements for the eDES.

- 3.2.3 The PD or designee will provide wording for successful enrollment email notifications and will identify the personnel to whom this email will be sent.
- 3.2.4 Assignment order of screening PIDs will be created by the designated biostatistician and MITS.

